3.4 Handling of Unscheduled or Repeated Measurements

Descriptive summaries and by-visit analyses will be presented according to the planned (scheduled) visits, unless otherwise specified. Discontinuation visits will be summarised at a scheduled visit providing the discontinuation visit occurs within the protocol specified visit windows. The protocol specified visit windows are to be completed.

In case data collection is done at an Unscheduled Visit rather than at the planned Assessment Visit, that measurement will be allocated to the nearest Assessment Visit. This allocation will be implemented in the Reporting Data Base.

4. STUDY PATIENTS

Study Patients data will be presented by descriptive statistics by treatment group and total. Continuous variables will be summarised by number of patients (n), mean, standard deviation (SD), minimum, median and maximum, while categorical variables by counts and percentages. Unless otherwise stated the calculation of proportions will be based on the size of the analysis set of interest.

Listings will include all enrolled patients unless specified otherwise.

Summaries for Study Patients variables will be provided for both the mITT and the safety analysis set.

4.1 Patient Disposition

The number and percentage of all patients screened, randomised, randomised who did not receive IMP, included in the safety analysis set, included in the modified ITT analysis set, prematurely discontinued IMP, prematurely withdrawn from the study, and patients who completed the study will be presented by treatment group and total.

The number and percentage of patients will be summarised by their reasons for withdrawal (including Adverse Event, Death, Recurrent Disease, High Manganese Within the CNS, Lack of Efficacy, Lost to follow up, Non-Compliance With Study Drug, Physician Decision, Pregnancy, Progressive Disease, Protocol Deviation, Recovery, Site Terminated by Sponsor, Study Terminated by Sponsor, Technical Problems, Withdrawal by Subject, Other).

Individual reasons for withdrawal will be presented in the listing.

4.2 Protocol Deviations

All responses to the inclusion and exclusion criteria and all protocol deviations will be listed by patient. All important protocol deviations may also be summarised by treatment group, total for pre-specified categories, as appropriate.

4.3 Background and Demographic Characteristics

Summaries for background and demographic characteristics will be provided for both the mITT and the safety analysis set.

4.3.1 Demography

Demographic characteristics (age [years], gender [male, female] and race [Asian, Black or African American, White]) and body measurements (height, weight and BMI) collected at Screening will be summarised for each treatment group and total.

Age (years) is calculated in years as: $\text{integer}(\text{date of first dose of IMP} - \text{date of birth})$.

Body Mass Index (BMI) is calculated as: $\text{Weight (kg)} / \text{Height (m)}^2$.

4.3.2 Medical History, Ongoing Medical Conditions and Prior Anti-cancer Therapy

Medical history and ongoing medical conditions will be coded using the MedDRA Dictionary, Version 23.0. The number and percentage of patients will be presented for ongoing conditions and previous conditions separately by system organ class (SOC) and preferred term (PT) for each treatment group and total. Also, the number and percentage of patients with prior anti-cancer therapy will be presented for each treatment group and total. All events will be listed by patient.

4.3.3 Prior and Concomitant Medications

Prior and concomitant medications will be coded using the WHO Drug Dictionary (WHODRUG GLOBAL B3 September 1, 2017). The number and percentage of patients will be presented for prior and concomitant medications separately by system organ class (SOC) and Anatomical Therapeutic Chemical (ATC) classification system for each treatment group and total. All events will be listed by patient.

4.3.4 ECOG Performance Status

The number and percentage of patients in the categories of the ECOG performance status (see Table 1) at baseline (time of administration of the first dose of IMP – day 1, cycle 1) will be presented by treatment group and total.

Table 1 ECOG Performance Status

Grade	ECOG status
0	Fully active, able to carry on all pre-disease performance without restriction
1	Restricted in physically strenuous activity but ambulatory and able to carry out work of a light or sedentary nature, e.g., light house work, office work
2	Ambulatory and capable of all selfcare but unable to carry out any work activities. Up and about more than 50% of waking hours
3	Capable of only limited selfcare, confined to bed or chair more than 50% of waking hours
4	Completely disabled. Cannot carry on any selfcare. Totally confined to bed or chair
5	Dead

4.3.5 ECG at Screening

The 12-lead electrocardiogram and QTcF interval is measured at screening only.

Data presentations

- Table: number (%) of patients with normal/abnormal ECG by treatment group and total.
- Table: descriptive statistics of QTcF by treatment group and total.

All observed values of the 12-lead ECG and QTcF will be listed by patient.

4.4 Administration of Investigational Medical Product and Chemotherapy

4.4.1 Investigational Medical Product (IMP)

The following variables related to the administration of IMP will be summarised and listed:

- Number and percentage of patients receiving IMP by cycle
- Cumulative dose of IMP
- Duration of IMP administration (weeks)
- Dose intensity (mL/week) = cumulative dose (mL) / treatment duration (weeks)
- Mean number of treatment cycles of IMP

Data presentations

- Table: number (%) of patients receiving IMP by treatment group and total for each treatment cycle
- Table: descriptive statistics of cumulative dose of IMP by treatment group and total
- Table: descriptive statistics of duration of IMP by treatment group and total
- Table: descriptive statistics of dose intensity of IMP by treatment group and total
- Table: descriptive statistics of number of treatment cycles of IMP by treatment group and total

All observed values of the administration of IMP will be listed by patient.

4.4.2 Oxaliplatin

The following variables related to the administration of oxaliplatin will be summarised and listed:

- Number and percentage of patients receiving oxaliplatin by cycle
- Cumulative dose of oxaliplatin (see also Section 5.3.3)
- Duration of oxaliplatin administration (weeks)
- Dose intensity ($\text{mg}/\text{m}^2/\text{week}$) = cumulative dose (mg/m^2) / treatment duration (weeks)
- Number and percentage of patients with dose modifications (reduced or delayed) of Oxaliplatin
- Duration of dose delay(s)
- Mean number of treatment cycles of Oxaliplatin

Data presentations

- Table: number (%) of patients receiving oxaliplatin by treatment group and total for each treatment cycle
- Table: descriptive statistics of cumulative dose of oxaliplatin by treatment group and total
- Table: descriptive statistics of duration of oxaliplatin by treatment group and total
- Table: descriptive statistics of dose intensity of oxaliplatin by treatment group and total
- Table: number (%) of patients with dose modifications (reduced or delayed) of oxaliplatin by treatment group and total for each treatment cycle
- Table: descriptive statistics of duration of dose delays of oxaliplatin by treatment group and total
- Table: descriptive statistics of number of treatment cycles of oxaliplatin by treatment group and total
- Figure: the proportion of patients receiving oxaliplatin will be graphically depicted (lineplot) vs treatment cycle/assessment visit by treatment group.

All observed values of the administration of oxaliplatin will be listed by patient.

4.4.3 5-FU

The following variables related to the administration of 5-FU (IV Bolus/IV Continued Infusion) will be summarised and listed:

- Number and percentage of patients receiving 5-FU by cycle
- Cumulative dose of 5-FU (see also Section 5.4.4)
- Duration of 5-FU administration (weeks)
- Dose intensity ($\text{mg}/\text{m}^2/\text{week}$) = cumulative dose (mg/m^2) / treatment duration (weeks)
- Number and percentage of patients with dose modifications (reduced or delayed) of 5-FU
- Duration of dose delay(s)
- Mean number of treatment cycles of 5-FU

Data presentations

- Table: number (%) of patients receiving 5-FU by treatment group and total for each treatment cycle
- Table: descriptive statistics of cumulative dose of 5-FU (IV Bolus/IV Continued Infusion) by treatment group and total
- Table: descriptive statistics of duration of 5-FU by treatment group and total
- Table: descriptive statistics of dose intensity of 5-FU (IV Bolus/IV Continued Infusion) by treatment group and total
- Table: number (%) of patients with dose modifications (reduced or delayed) of 5-FU by treatment group and total for each treatment cycle
- Table: descriptive statistics of duration of dose delays of 5-FU by treatment group and total
- Table: descriptive statistics of number of treatment cycles of 5-FU by treatment group and total

All observed values of the administration of 5-FU (IV Bolus/IV Continued Infusion) will be listed by patient.

4.4.4 Calcium-folate or Calcium-levofolate

The following variables related to the administration of Calcium-folate or Calcium-levofolate will be summarised and listed:

- Number and percentage of patients receiving Calcium-folate or Calcium-levofolate by cycle
- Cumulative dose of Calcium-folate or Calcium-levofolate
- Duration of Calcium-folate or Calcium-levofolate administration (weeks)
- Dose intensity ($\text{mg}/\text{m}^2/\text{week}$) = cumulative dose (mg/m^2) / treatment duration (weeks)
- Number and percentage of patients with dose modifications (reduced or delayed) of Calcium-folate or Calcium-levofolate
- Mean number of treatment cycles of Calcium-folate or Calcium-levofolate

Data presentations

- Table: number (%) of patients receiving Calcium-folate or Calcium-levofolate by treatment group and total for each treatment cycle
- Table: descriptive statistics of cumulative dose of Calcium-folate or Calcium-levofolate by treatment group and total
- Table: descriptive statistics of duration of Calcium-folate or Calcium-levofolate by treatment group and total
- Table: descriptive statistics of dose intensity of Calcium-folate or Calcium-levofolate by treatment group and total
- Table: number (%) of patients with dose modifications (reduced or delayed) of Calcium-folate or Calcium-levofolate by treatment group and total for each treatment cycle
- Table: descriptive statistics of number of treatment cycles of Calcium-folate or Calcium-levofolate by treatment group and total

All observed values of the administration of Calcium-folate or Calcium-levofolate will be listed by patient.

5. EFFICACY EVALUATION

Unless otherwise stated, all efficacy variables will be analysed using the MITT analysis set. The general principles for handling unscheduled or repeated measurements is described in Section 3.4.

5.1 Primary Endpoint

5.1.1 Moderate to Severe CIPN

The primary endpoint is defined as the proportion of patients (with moderate or severe chronic CIPN) scoring 3 or 4 in at least 1 of the first 4 items of the FACT/GOG-NTX-13 (i.e., FACT/GOG-NTX-4), targeting numbness, tingling or discomfort in hands and/or feet, 9 months after the first dose of IMP (i.e. PledOx or placebo administered on Day 1, Cycle 1 of mFOLFOX6 chemotherapy).

Baseline is defined as the time of administration of the first dose of IMP (Day 1, Cycle 1).

Moderate to Severe CIPN will derived (SAS) as follows:

```
cipn=0;  
IF ntx1_std=. AND ntx2_std=. AND ntx3_std=. AND ntx4_std=. THEN cipn=.;  
ELSE IF ntx1_std IN('3','4') OR ntx2_std IN('3','4') OR  
      ntx3_std IN('3','4') OR ntx4_std IN('3','4') THEN cipn=1;
```

Primary Analysis – Cochran-Mantel-Haenszel. The primary analysis of the primary endpoint Moderate to Severe CIPN (yes/no) at 9 months after first dose of IMP will be analysed by the Cochran-Mantel-Haenszel (CMH) estimate of the common relative risk of Moderate to Severe CIPN. The treatment effect will be assessed by estimating the ratio of the incidence rates of CIPN in PledOx 5µmol/kg versus Placebo along with its 95% confidence interval and corresponding p-value. The CMH estimate will be adjusted for cumulative exposure of oxaliplatin and stratified by study and region. Incidence rates (95% CIs) for each treatment will also be presented.

Notations. The combined analysis includes two studies (POLAR-A and POLAR-M) and two geographical regions (Asia/Non-Asia), and so there are 4 strata, where

- 1 = POLAR-A / Asia
- 2 = POLAR-A / Non-Asia
- 3 = POLAR-M / Asia
- 4 = POLAR-M / Non-Asia

Treatments are denoted by 1 and 2, where 1 = PledOx 5µmol/kg and 2 = Placebo. For treatment j in the i^{th} strata the cumulative exposure of oxaliplatin is T_{ij} and E_{ij} is CIPN events. Let $T_{i\bullet} = T_{i1} + T_{i2}$ and $E_{i\bullet} = E_{i1} + E_{i2}$ denote total cumulative exposure of oxaliplatin and total CIPN events in the i^{th} strata.

CMH point estimate of the common relative risk across strata. Under $H_0: R_1 = R_2 = R$, Breslow and Day [1] provide the stratified Cochran-Mantel-Haenszel estimate of the common relative risk as

$$\hat{R}_{M-H} = \frac{\sum_{i=1}^k \frac{E_{i1}T_{i2}}{T_{i\bullet}}}{\sum_{i=1}^k \frac{E_{i2}T_{i1}}{T_{i\bullet}}}$$

Also, Robins, Breslow and Greenland [2] provide an estimate of the variance of $\log \hat{R}_{M-H}$ as

$$\hat{V}[\log(\hat{R}_{M-H})] = \frac{\sum_{i=1}^k \frac{T_{i1} T_{i2} E_{i\bullet}}{T_{i\bullet}^2}}{\hat{R}_{M-H} \left\{ \sum_{i=1}^k \frac{T_{i1} T_{i2} E_{i\bullet}}{T_{i\bullet} (T_{i2} + T_{i1} \hat{R}_{M-H})} \right\}^2}$$

Then, a 95% confidence interval for the common relative risk across strata is,

$$\exp \{ \log(\hat{R}_{M-H}) \pm 1.96 \times SE \}$$

where $SE = \sqrt{\hat{V}[\log(\hat{R}_{M-H})]}$.

The statistic $Z = \frac{\log(\hat{R}_{M-H})}{SE} \sim N(0,1)$ so the 2-sided p-value is calculated by $2 \times (1 - CDF(|z|))$.

CMH event rates for each treatment. The Cochran-Mantel-Haenszel oxaliplatin exposure weighted incidence rate estimate for treatment j across strata is given by

$$U_j = \frac{\sum_{i=1}^k w_i \lambda_{ij}}{\sum_{i=1}^k w_i}, \quad j=1,2 \quad \text{and} \quad \lambda_{ij} = \frac{E_{ij}}{T_{ij}} \quad (\text{i.e the event rate for treatment } j \text{ in strata } i) \text{ and}$$

$$w_i = \frac{2}{\frac{1}{T_{i1}} + \frac{1}{T_{i2}}} \quad (\text{i.e. the harmonic mean cumulative exposure of oxaliplatin in strata } i).$$

CMH variance of the event rates. The variance of Cochran-Mantel-Haenszel oxaliplatin exposure weighted incidence rate estimate for treatment j across strata is given by

$$\text{Var}[U_j] = \text{Var} \left[\frac{\sum_{i=1}^k w_i \lambda_{ij}}{\sum_{i=1}^k w_i} \right] = \frac{\sum_{i=1}^k w_i^2 \text{Var}(\lambda_{ij})}{\left(\sum_{i=1}^k w_i \right)^2}$$

and hence

$$\hat{\text{Var}}[U_j] = \frac{\sum_{i=1}^k w_i^2 \text{Var}(\hat{\lambda}_{ij})}{\left(\sum_{i=1}^k w_i \right)^2} = \frac{\sum_{i=1}^k w_i^2 \frac{\hat{\lambda}_{ij}^2}{E_{ij}}}{\left(\sum_{i=1}^k w_i \right)^2} = \frac{\sum_{i=1}^k w_i^2 \frac{E_{ij}}{T_{ij}^2}}{\left(\sum_{i=1}^k w_i \right)^2}$$

Further,

$$\text{Var}[\log(U_j)] = \frac{1}{U_j^2} \text{Var}[U_j] = \frac{\left(\sum_{i=1}^k w_i \right)^2}{\left(\sum_{i=1}^k w_i \lambda_{ij} \right)^2} \times \frac{\sum_{i=1}^k w_i^2 \text{Var}(\lambda_{ij})}{\left(\sum_{i=1}^k w_i \right)^2} = \frac{\sum_{i=1}^k w_i^2 \text{Var}(\lambda_{ij})}{\left(\sum_{i=1}^k w_i \lambda_{ij} \right)^2}$$

and so

$$\hat{\text{Var}}[\log(U_j)] = \frac{\sum_{i=1}^k w_i^2 \text{Var}(\hat{\lambda}_{ij})}{\left(\sum_{i=1}^k w_i \hat{\lambda}_{ij}\right)^2} = \frac{\sum_{i=1}^k w_i^2 \frac{\hat{\lambda}_{ij}^2}{E_{ij}}}{\left(\sum_{i=1}^k w_i \hat{\lambda}_{ij}\right)^2} = \frac{\sum_{i=1}^k w_i^2 \frac{E_{ij}}{T_{ij}^2}}{\left(\sum_{i=1}^k w_i \frac{E_{ij}}{T_{ij}}\right)^2}$$

Then, a 95% confidence interval for the Cochran-Mantel-Haenszel oxaliplatin exposure weighted incidence rate estimate across strata is,

$$U_j \times \exp \left\{ \pm 1.96 \sqrt{\widehat{\text{Var}}[\log(U_j)]} \right\}$$

Interpretation of parameter estimates. The Cochran-Mantel-Haenszel method provide estimates of oxaliplatin-dose adjusted Moderate to Severe CIPN event rates at 9 months. The associated unit of measurement for the CMH estimates is therefore the CIPN event rate per unit dose of oxaliplatin. To aid in clinical interpretation and understanding, the CMH estimates will be scaled to a relevant clinical dose eg 800 mg/m² to allow the event rate to be expressed per 100 patients relative to this dose. It can also be used to represent the number of events saved when receiving active treatment as compared to placebo. The example data below illustrates this in more detail.

The exact same interpretation can be done for the event rates (LSmeans) estimated from the negative binomial model as described further below.

Table 2 Example data

	Placebo	PledOx 5 µmol/kg	
No CIPN	70 (59%)	86 (73%)	156
CIPN	48 (41%)	32 (27%)	80
	118	118	236

Table 3 Example data: Cochran-Mantel-Haenszel estimates of Moderate to severe CIPN 9 months after first dose of IMP

	N	Estimate	95% CI	P-value
PledOx 5 µmol/kg	118	0.000317	[0.000222; 0.000454]	-
Placebo	118	0.000462	[0.000343; 0.000623]	-
PledOx 5 µmol/kg vs Placebo	236	0.6869	[0.4391; 1.0745]	0.0999

Suppose the mean cumulative dose overall of oxaliplatin is 800 mg/m² so the event rates are estimated by:

PledOx 5 µmol/kg 0.000317 x 800 = 0.25 CIPN events per patient per 800 mg/m² of oxaliplatin

Placebo 0.000462 x 800 = 0.37 CIPN events per patient per 800 mg/m² of oxaliplatin

This translates into:

PledOx 5 µmol/kg 25 CIPN events per 100 patients treated

Placebo 37 CIPN events per 100 patients treated

This represents a saving of 12 CIPN events per 100 patients treated with PledOx 5 µmol/kg.

In the results presentation of the CSR the observed mean cumulative dose of oxaliplatin will be used.

Supportive Analysis of the primary endpoint - Negative Binomial Regression. A supportive analysis of the primary endpoint Moderate to Severe CIPN (yes/no) at 9 months after first dose of IMP will be analysed by a negative binomial regression model adjusted for study (POLAR-A / POLAR-M) and region (Asia / non-Asia). An offset variable will also be used to adjust for the oxaliplatin exposure defined as the logarithm of the cumulative dose of oxaliplatin received by each patient. Estimate of the treatment contrast (rate ratio) and its corresponding 95% confidence interval will be based on the anti-log of the model parameter estimate and CI.

SAS Code Example Negative Binomial Regression using PROC GENMOD

```
PROC GENMOD;
  CLASS study region trt;
  MODEL cipn = study region trt/DIST=negbin LINK=log SCALE=deviance OFFSET=log_exp;
  ESTIMATE 'PledOx 5 µmol/kg vs Placebo' trt 1 -1;
  LSMEANS trt / CL EXP;
RUN;
```

If convergence criterion is not met using PROC GENMOD an alternative using PROC NLMIXED will be used.

SAS Code Example Negative Binomial Regression using PROC NLMIXED

```
PROC NLMIXED;
  PARMs b0 -2 b1 .1 b2 -.01 b3 .1 phi .1;
  eta = log_exp + b0 + b1*(study=1) + b2*(region=1) + b3*(trt=0);
  mu = exp(eta);
  LL = y*log(phi*mu) - (y+(1/phi))*log(1+(phi*mu)) + lgamma(y+(1/phi)) -
lgamma(1/phi) - lgamma(y+1);
  MODEL y ~ general(LL);
RUN;
```

Exploratory Analysis – Exact Logistic Regression. An exploratory analysis of the primary endpoint Moderate to Severe CIPN at 9 months after first dose of IMP will be analysed by exact logistic regression model adjusted for study (POLAR-A / POLAR-M) and region (Asia / non-Asia). Estimate of the treatment effect and its corresponding 95% confidence interval will be based on the odds-ratio.

SAS Code Example Exact Logistic Regression

```
PROC LOGISTIC DESC;
  CLASS study region trt(ref='0: Placebo');
  MODEL cipn = study region trt;
  EXACT trt;
RUN;
```

Using the same example data presented above, a crude estimate of the odds-ratio then is:

$$(0.27/0.73) / (0.41/0.59) = 0.53$$

Table 4 Example data: Exact Logistic Regression of Moderate to severe CIPN 9 months after first dose of IMP

	N	CIPN (%)	Odds-ratio	95% CI	P-value
PledOx 5 µmol/kg	118	27.1	-	-	-
Placebo	118	40.7	-	-	-
PledOx 5 µmol/kg vs Placebo	236	-	0.54	[0.31;0.94]	0.0293

Data Presentations

- Table: the primary analysis of Moderate to Severe CIPN based on the Cochran-Mantel-Haenszel estimate will be presented by number of patients (N), treatment estimates and its 95% CIs. The rate ratio between PledOx 5 µmol/kg and Placebo will be presented by the estimate, 95% CI and p-value.
- Table: the supportive analysis of Moderate to Severe CIPN based on the negative binomial regression model will be presented by number of patients (N), treatment estimates and its 95% CIs. The rate ratio between PledOx 5 µmol/kg and Placebo will be presented by the estimate, 95% CI and p-value.
- Table: the number and percentage of patients with Moderate to Severe CIPN along with its 95% CI presented by treatment group and total for each treatment visit/assessment visit. The confidence intervals will be based on the method of Clopper-Pearson (exact).
- Table: the exploratory analysis of Moderate to Severe CIPN based on the exact logistic regression model will be presented by number of patients (N), number of patients (%) with Moderate to Severe CIPN at 9 months after first does of IMP for each treatment group, and odds-ratio, 95% CI and p-value for the treatment comparison.
- Figure: the proportion (including 95% CIs) of patients with Moderate to Severe CIPN will be graphically depicted (lineplot) vs treatment cycle/assessment visit by treatment group.
- All observed values of Moderate to Severe CIPN will be listed by patient.

Missing values of the primary endpoint will be handled as described in Section 5.2.

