5.2 Handling of Missing Data in the Primary Endpoint

For the primary endpoint Moderate to Severe CIPN (yes/no) the following methods of imputation will be used for the primary analysis in case of missing:

1. Observed cases (no imputation)
2. “Non-responder” if missing (ie 3 or 4 on FACT/GOG)
3. Tipping point analysis – combinations of missing data values that would change the conclusion. References eg Yan (2009), Rubin (2012)

A tipping point analysis assesses the potential impact of informative missingness by progressively penalizing patients with missing data in the experimental arm. The goal is to find the level of penalization that results in loss of statistical significance on the primary endpoint.

The steps to perform the tipping point analysis are as follows:

1. The NB model as described in Section 5.1.1 is applied to each randomised treatment arm separately based on the observed data in that arm. This will give two parameters for each of the experimental and control groups, the event rate, μ , and the dispersion rate, κ .
2. For each subject, i , in the experimental arm who had $t_i < 9$ months follow-up and who did not record a primary endpoint event in the period $(0 - t_i]$, simulate their event rate, μ_i , by randomly sampling an observation from a $Gamma(shape = 1/\kappa, scale = 1/(\kappa\mu))$ distribution.
3. Using μ_i , the time to event for subject i in the period $(t_i, 9]$ is given by $\Delta_i = -\ln(1 - \omega_i)/\mu_i$ where ω_i is a random deviate from a $U(0,1)$ distribution.
4. If $t_i + \Delta_i \leq 9$ then subject i is considered to have had an event at with an exposure time of $t_i + \Delta_i$. If $t_i + \Delta_i > 9$ then subject i is considered not to have event at with an exposure time of 9 months.
5. Steps 2-4 will result in a full dataset with no missing primary endpoint data over the period (0-9] months.

6. This full dataset is then analysed in the same manner as described for the primary endpoint using the Cochran-Mantel-Haenszel approach and the treatment effect and associated SE are estimated.
7. Steps 2-6 are repeated multiple times and the resulting treatment effect estimates and SEs are combined in SAS via PROC MIANALYZE using Rubin's rules. This will provide the estimated treatment effect having imputed missing data under a missing at random assumption.

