5.3 Secondary Efficacy Endpoints

5.3.1 Mild to Severe CIPN

Proportion of patients (with mild, moderate or severe chronic CIPN) scoring 2, 3, or 4, in at least 1 of the first 4 items of the FACT/GOG-NTX-13 (i.e. FACT/GOG-NTX-4), targeting numbness, tingling or discomfort in hands and/or feet, 9 months after the first dose of IMP.

Baseline is defined as the time of administration of the first dose of IMP (Day 1, Cycle 1).

Mild to Severe CIPN will derived (SAS) as follows:

```
cipn2=0;  
IF ntx1_std=. AND ntx2_std=. AND ntx3_std=. AND ntx4_std=. THEN cipn2=.;  
ELSE IF ntx1_std IN('2','3','4') OR ntx2_std IN('2','3','4') OR  
      ntx3_std IN('2','3','4') OR ntx4_std IN('2','3','4') THEN cipn2=1;
```

Mild to Severe CIPN will be analysed using the method of Cochran-Mantel-Haenszel as described in detail in Section 5.1.1.

Data Presentations

- Table: the analysis of Mild to Severe CIPN based on the negative binomial regression model will be presented by number of patients (N), treatment estimates and its 95% CIs. The rate ratio between PledOx 5 $\mu\text{mol/kg}$ and Placebo will be presented by the estimate, 95% CI and p-value.
- Table: the number and percentage of patients with Mild to Severe CIPN along with its 95% CI presented by treatment group and total for each treatment visit/assessment visit. The confidence intervals will be based on the method of Clopper-Pearson (exact).
- Figure: the proportion (including 95% CIs) of patients with Mild to Severe CIPN will be graphically depicted (lineplot) vs treatment cycle/assessment visit by treatment group.
- All observed values of Mild to Severe CIPN will be listed by patient.

All the analyses of Mild to Severe CIPN will be based on the observed cases. Hence, no imputation of missing values will be done.

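### A partly blank neuropathy form with no answered item at 3 or 4 is coded as no CIPN, and stays so even in the analysis that counts missing as CIPN

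*SAP*

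**What the plan says.** SAP Section 5.1.1 defines the primary endpoint as "scoring 3 or 4 in at least 1 of the first 4 items of the FACT/GOG-NTX-13", assessed 9 months after the first dose of IMP. The SAS derivation has three steps:

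- `cipn` starts at 0.
- It becomes missing under one condition only, that all four items are blank: "IF ntx1_std=. AND ntx2_std=. AND ntx3_std=. AND ntx4_std=. THEN cipn".
- Otherwise it becomes 1 if any answered item is 3 or 4: "ELSE IF ntx1_std IN('3','4') OR ntx2_std IN('3','4') OR" and so on for the other two items.

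Section 5.2 then says, for the yes/no endpoint, that "the following methods of imputation will be used for the primary analysis in case of missing". Method 1 is "Observed cases (no imputation)". Method 2 counts the patient as a non-responder "if missing (ie 3 or 4 on FACT/GOG)". Method 3 is a tipping-point analysis. Its imputation applies to patients with less than 9 months of follow-up "who did not record a primary endpoint event in the period" up to that time.

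The all-four-blank condition recurs in Section 5.3.1 ("IF ntx1_std=. AND ntx2_std=. AND ntx3_std=. AND ntx4_std=. THEN cipn2"), Section 5.3.7 (long-term CIPN) and Section 5.4.1 (any CIPN). Section 3.3 covers baseline values and incomplete dates. The SAP has no rule for single unanswered items.

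**The concern.** With an any-of-four endpoint, one item at 3 or 4 proves an event. The absence of an event is proven only when all four items are answered below 3. A blank item on a form with no answered 3 or 4 leaves the patient's status unknown, yet the code records it as known and favourable. In effect each blank is imputed as 0 to 2, which can hide an event but never create one.

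The inconsistency shows most clearly in method 2 of Section 5.2. A patient who leaves all four items blank is counted as having CIPN. A patient who answers one item with 0 and leaves three blank is counted as free of it. The purpose of method 2 is to count unknown outcomes as CIPN, and for this group it does the reverse. The tipping-point analysis does not catch them either, because it selects on length of follow-up and not on blanks in a 9-month form.

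**Working it through.** **1. What the code does to every possible form.** Each item is blank or scored 0 to 4, giving 6^4 = 1,296 patterns. With k blanks there are C(4,k) × 5^(4−k) patterns, of which C(4,k) × 3^(4−k) have no answered 3 or 4.

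| Blanks | Coded 0 | Coded 1 | Coded missing |
|---|---|---|---|
| 0 | 81 | 544 | 0 |
| 1 | 4 × 27 = 108 | 392 | 0 |
| 2 | 6 × 9 = 54 | 96 | 0 |
| 3 | 4 × 3 = 12 | 8 | 0 |
| 4 | 0 | 0 | 1 |

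Of the 500 + 150 + 20 = 670 partial patterns, 108 + 54 + 12 = 174 are coded no CIPN, 496 are coded CIPN and none is coded missing. These are counts of patterns, not of patients. They show that no partial form can reach the rules of Section 5.2.

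**2. How often such a form hides an event.** The SAP has no data on this, so a model is assumed: four exchangeable items on a latent normal scale, correlation 0.5 to 0.85, blanks at random. The true any-item event rate p is 27% (the PledOx example rate in Table 2) or 40% (the placebo design rate in Section 2.4). Let a be the probability that the answered items show no 3 or 4. The share of event-free partial forms hiding an event is (a − (1 − p)) / a.

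- One blank: 3% to 8%.
- Two blanks: 7% to 17%.
- Three blanks: 13% to 27%.

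Highest case (p = 0.40, correlation 0.5, three blanks): a = 0.826, so (0.826 − 0.600) / 0.826 = 27%.

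**3. Effect on the event rate.** If a fraction f of forms is partial, the coded rate falls by f × (a − (1 − p)). With f = 5% (assumed):

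- lowest (p = 0.27, correlation 0.85, one blank): 0.05 × 0.0226 = 0.1 point;
- highest (p = 0.40, correlation 0.5, three blanks): 0.05 × 0.2263 = 1.1 points;
- all one-blank cases: 0.1 to 0.3 point.

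**4. Effect on the ratio.** Take the simple risk ratio 0.27 / 0.40 = 0.675, without the oxaliplatin denominator.

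- Same f in both arms: 0.673 to 0.674 at f = 5% and 0.671 to 0.674 at f = 10%, a shift of at most 0.004.
- f = 10% in the PledOx arm only, correlation 0.5: with one blank (0.27 − 0.10 × 0.0416) / 0.40 = 0.665; with three blanks (0.27 − 0.10 × 0.1647) / 0.40 = 0.634.

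**5. Effect on method 2, using the SAP's example.** Table 3 is reproduced first. Events are 32 (PledOx) and 48 (placebo). Exposures implied by the rounded rates are 32 / 0.000317 = 100,946 and 48 / 0.000462 = 103,896. The ratio is (32 × 103,896) / (48 × 100,946) = 0.686. With one stratum the SAP's variance reduces to 1/32 + 1/48, so SE = 0.228, 95% CI 0.439 to 1.073, p = 0.099. The SAP states 0.6869, 0.4391 to 1.0745, p = 0.0999; the gap is rounding.

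Next, suppose some patients coded 0 in each arm have incomplete event-free forms and method 2 counts them as CIPN, with exposure unchanged:

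| Such forms, PledOx / placebo (assumed) | Rate ratio | p |
|---|---|---|
| 0 / 0 (as the code now treats them) | 0.686 | 0.099 |
| 2 / 2 | 0.700 | 0.108 |
| 5 / 5 | 0.719 | 0.123 |
| 10 / 10 | 0.745 | 0.147 |
| 5 / 2 | 0.762 | 0.209 |
| 2 / 5 | 0.660 | 0.059 |

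**The case against.** A reader might infer that every partly blank form counts as a treatment success. The code does not do that. A partial form with an answered 3 or 4 is coded CIPN, and rightly so, because one such item meets the definition.

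A reader might also infer a tilt towards PledOx. The SAP does not support that. The rule is identical in both arms, and with equal proportions of partial forms the lost events nearly cancel in the ratio. A material bias needs an imbalance between arms, which nothing in the SAP shows.

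The number of partial forms is also unknown, and the SAP does not say whether data capture allows them. If there are none, nothing changes. The upper figure of 1.1 points needs every partial form to have three blanks. All of this stands, and it limits the point to a small one.

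The parenthesis in method 2 could be read as imputing 3 or 4 for each blank item, which would solve the problem. But the sentence introducing the methods concerns the yes/no endpoint when it is missing, and the code never makes these forms missing.

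Finally, counting incomplete event-free forms as CIPN will be wrong for most of them: under the model, 92% to 97% of those with one blank are true non-events. That is a fair cost, but it is the nature of a missing-as-CIPN analysis, which makes the same deliberate assumption for fully blank forms.

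**Conclusion.** The point holds for forms with one to three blanks and no answered item at the event threshold. They are coded as known non-events when their status is unknown, and they bypass all three methods of Section 5.2. The missing-as-CIPN analysis of the primary endpoint is therefore not worst-case for them. The same coding enters the observed-case results for mild-to-severe, long-term and any CIPN.

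The size is small: an under-count of about 0.1 to 1.1 percentage points if 5% of forms are partial, and a shift in the risk ratio of at most 0.004 with up to 10% partial forms spread equally over the arms. These figures rest on the assumed frequency, the assumed item correlation and blanks at random. The coding result in step 1 rests on no assumption. This is a worthwhile correction and not a threat to the primary comparison.

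**What to change.** In Sections 5.1.1 and 5.2:

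- Keep `cipn=1` whenever any answered item is 3 or 4, however many items are blank.
- Flag a form as incomplete when `cipn=0` and one to three items are blank, for example `inc=(cipn=0 AND 1<=CMISS(OF ntx1_std ntx2_std ntx3_std ntx4_std)<=3)`.
- In method 2, count the patient as CIPN if `cipn` is missing or `inc=1`.
- Tabulate flagged forms by arm and number of blanks, so that any imbalance is visible.
- State that observed cases keep the present coding, and say the same for Sections 5.3.1, 5.3.7 and 5.4.1, which use no imputation.

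Two alternatives are worse. Setting `cipn` to missing whenever too few items are answered, whatever they show, discards confirmed events. Dropping only the event-free partial forms from observed cases leaves nothing but events among the partial forms.

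The cost is a few lines of derivation code and one table, to be settled before the blind is broken. Method 2 becomes slightly more conservative, since most flagged forms, especially those with one blank, are probably true non-events.
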